OFFICIAL TITLE OF THE STUDY:

A SINGLE CENTER EXPERIENCE: SAFETY AND EFFICACY OF DEB-TACE PERFORMED WITH A NOVEL REFLUX-CONTROL MICROCATHETER IN PATIENTS WITH EARLY AND INTERMEDIATE HCC.

NCT Number : Not available

Date of the document : October/ 20/ 2020.

BACKGROUND:

Hepatocellular carcinoma is the fifth most frequent cancer in the world, with a diagnosis of more than 500,000 new cases per year. It is considered the third leading cause of cancer mortality and presents well-defined risk factors. Liver cirrhosis is the main risk factor for developing HCC, therefore screening programs in cirrhotic patients will allow the early diagnosis of this neoplasia. Despite this, most HCCs are diagnosed at a stage in which the application of curative therapies is no longer possible.

Hepatic transarterial chemoembolization (TACE) belongs to the arterially directed embolization therapies for the treatment of unresectable early-to-advanced hepatocellular carcinoma (HCC). It is the only therapy that has shown to improve survival in intermediate-stage HCC.

Drug-eluting beads (DEB)-TACE has shown to provide slow drug elution, reduced liver and systemic toxicity, increased local drug concentration, and tissue necrosis.

Aside from TACE, other transarterial options include bland embolization, or hepatic artery embolization (HAE), and transarterial radioembolization (TARE). All have an acceptable safety profile, and each has its associated procedural and peri-procedural complications. One potential complication that may occur during all embolization procedures is when the embolic material migrates outside of the desired treatment area, leading to non-target embolization (NTE). In fact, when collateral vessels are embolized, there is a risk that these may be feeders of non-target tissue or organs. NTE following TACE in particular may lead to a double-layer problem: dangerous components affecting healthy tissue, one ischemic and one related to cytotoxicity from the chemotherapeutic agent, which may have clinical consequences, and potential incomplete treatment of the lesion (due to beads being "deviated" from target).

NTE is highly recognized, but often thought to be uncommon, and although different complications can be caused by it, there may appear to be no evidence of NTE during the intraprocedural imaging.

To avoid the complications due to NTE, apart from the importance of the pre, intra and post-procedural imaging, and the thorough study of the anatomical picture, the catheters/microcatheters should also be chosen with reason and care. In particular, selective catheterization should be achieved by placing the microcatheter tip as close as possible to the target, through the specific branch/branches supplying it.

However, even with the microcatheter selectively positioned in the vessel to be embolized, the risk of NTE might not be eliminated, since it could happen as a result of changes in flow dynamics that occur during embolization, particularly when the endpoint is stasis. These changes could result in reflux into non-target territories and, as such, might be better prevented with the use of microcatheters intended to reduce reflux. To this purpose, the use of a dedicated delivery device should be taken into consideration, in order to optimize and save time during the procedure.

Microcatheters are commonly used during most arterial embolization procedures, and as explained above, there is a strong rationale to use a reflux-control microcatheter – like SEQUIRE® (Guerbet, Roissy-France) – for DEB-TACE.

The main expectation is to achieve technical success with SEQUIRE[®] in all patients with a reachable target lesion, with the intent not only to minimize potential damage to surrounding tissue, but also to potentially deliver more treatment embolics, as all the beads are (re)directed towards the target.

The use of small diameter particles (100 micron-TANDEM[®] spheres- Varian Medical Devices, Palo Alto, CA, US), induces superior tumor necrosis response (*Urbano et al.*, European Journal of Radiology, 2020); with the synergistic effect of being administered through the SEQUIRE anti-reflux protection system, there is reason to believe that it will be possible to administer maximum doses of doxorubicin, while avoiding the occlusion of non-target arterial segments (SYNERGIC EFFECT).

STUDY PROPOSAL:

Investigators propose a prospective observational study with data collection from a single center (Virgen de las Nieves University Hospital-Granada), for a period that ranges October 2020-December 2021. Here summarized the inclusion criteria and contraindications:

Inclusion criteria

- BCLC B and or some case BCLC A
- Both genders
- Over 18 years.
- Bilirubin less than 3 gr/dl.
- No contraindications to the use of iodinated contrast
- Absence of chronic kidney disease
- ECOG 0-1.
- Absence of encephalopathy.
- Informed consent.

Contraindications

- Advanced liver disease.
- Thrombosis or reversal of portal flow.
- Vascular invasion.
- Extrahepatic spread.
- Contraindication to administration of cytostatics.
- Contraindication to angiographic procedure.

HYPOTHESIS:

The use of 100 micron-TANDEM[®] spheres will be studied with the synergistic effect of being administered through SEQUIRE[®] microcatheter anti-reflux protection system, which may allow the administration of the maximum doses of doxorubicin, avoiding the undesired occlusion of collateral arterial segments (SYNERGIC EFFECT). Other variables to study are: access route, procedural time and fluoroscopy time.

The information will be collected through the electronic database of the patient (includes laboratory data). Patients will be evaluated starting from the date of inclusion as candidates for TACE treatment, and followed up for 6 months (unless patients are lost to clinical follow-up or death occurs). Mortality data are obtainable by searching the electronic history of the patient.

Changes in the serum levels of aspartate aminotransferase (AST), alanine aminotransferase (ALT), Alkaline phosphatase (ALP), bilirubin, albumin and patients' complete hematological profile, as well as serum lipase and amylase levels within the 1st week post-TACE to detect pancreatitis, will be evaluated at the following time-points: pre-embolization, at one month, three months, and six months. Computed tomography (CT) or Magnetic Resonance Imaging (MRI) with contrast will be performed at the same time-points as just indicated; modified Response Evaluation Criteria in Solid Tumors (m-RECIST) will be used, and images will be assessed by two experienced radiologists (any discordant interpretation will be solved through team consensus). All serologic toxicities would be classified according to common terminology criteria for adverse effects. On this scale, severe hepato-toxicity (grade 3) is classified as the increase of up to 5 times the normal limit of AST, ALT, FA or the increase of bilirubin level to over 3 g/dl.

PATIENT SELECTION:

Between October 2020 and December 2021, and expected number of 30 patients will be treated. The diagnosis of Hepatocellular carcinoma (HCC) will confirm in accordance with the American Association for the Study of Liver Diseases guidelines and HCC staged according to Barcelona Clinic Liver Cancer (BCLC) system.

DEB-TACE is indicated according to clinical practice guidelines referred above.

TECHNICAL PROCEDURE:

The embolization will be performed using TANDEM[®] spheres (each cc of spheres can be loaded with up to 50 mg of doxorubicin. The maximum dose of doxorubicin used per procedure was 150 mg, corresponding to 3 cc of spheres) and SEQUIRE[®] microcatheter in a super-selective tumour's arterial position avoiding undesired arterial branches. The procedure will consider super-selective when the micro-catheter tip reached the tumour feeding artery. Each cc of microspheres will mix with 7-10 cc of non-ionic contrast medium. Embolization endpoint is considered vascular stasis or 150 mg of Doxorubin administered.

OBJECTIVES AND END-POINTS:

Efficacy:

[figure not shown]
- Technical success will be defined as a composite outcome measurement: ability to place the microcatheter inside the required vascular segment and qualitative assessment of microspheres deposition in the target tumour.

- Time to Progression (TTP) [Time Frame: 6 months]. Time at which progression is first observed in a tumor assessment according to mRECIST as assessed by CT or MRI.
- Objective Response Rate (ORR) and Disease Control Rate (DCR) [Time Frame: Assessed at 1, 3, and 6 months after first treatment]. ORR is defined as a complete or partial response among the total number of cases and DCR is defined as a complete, partial response or stable disease among the total number of cases, according to mRECIST evaluated by CT or MRI. Time to retreatment included as consequential secondary objective.

Safety:

- Adverse Events (AEs) and Serious Adverse Events (SAE) [Time Frame: Assessed at 1, 3, and 6 months after first treatment. The incidence of emerging AE and SAE will be summarized according to standardized qualification criteria [Journal of Vascular Interventional Radiology (JVIR) SAE], including pancreatitis, cholecystitis, clinical presentations, postembolization syndrome (PES), etc.
- Non Target embolization (NTE) by thorough angiographic assessment of the whole liver vasculature after TACE, as well as Cone Beam Computed Tomography (CBCT) **performed immediately following embolization (within 30 minutes from the end of procedure) to evaluate off-target distribution.**
- Health-Related Quality of Life questionnaire (HRQOL): pre-treatment and post-treatment quality of life assessment using the specific questionnaire for functional assessment for cancer treatment (FACT-G).

Study flowchart

SECONDARY OBJECTIVES:
1-TTP
2-HRQOL
3-Time to retreatment

DEB-TACE PROCEDURES:

The embolization will be performed according to routine clinical practice, with drug-eluting microspheres (100-micron TANDEM[®] spheres), pre-loaded with 50 mg doxorubicin per ml (1 syringes of 3 ml). Injection will be according to manufacturer recommendations, with a selective or superselective approach depending on lesion and feeder localization.

RECIST	mRECIST for HCC
CR = Disappearance of all target lesions	CR = Disappearance of any intratumoral arterial enhancement in all target lesions
PR = At least a 30% decrease in the sum of diameters of target lesions, taking as reference the baseline sum of the diameters of target lesions	PR = At least a 30% decrease in the sum of diameters of viable (enhancement in the arterial phase) target lesions, taking as reference the baseline sum of the diameters of target lesions
SD = Any cases that do not qualify for either partial response or progressive disease	SD = Any cases that do not qualify for either partial response or progressive disease
PD = An increase of at least 20% in the sum of the diameters of target lesions, taking as reference the smallest sum of the diameters of target lesions recorded since treatment started	PD = An increase of at least 20% in the sum of the diameters of viable (enhancing) target lesions, taking as reference the smallest sum of the diameters of viable (enhancing) target lesions recorded since treatment started

AASLD, American Association for the Study of Liver Diseases; JNCI, Journal of the National Cancer Institute; HCC, hepatocellular carcinoma; mRECIST, modified Response Evaluation Criteria in Solid Tumors; CR, complete response; PR, partial response; SD, stable disease; PD, progressive disease.

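### Does giving the same dates for data collection and for treatment cut off the 6-month results of patients treated late?

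*Protocol*

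**What the plan says.** Four statements in the protocol bear on the calendar.

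- **Study Proposal** describes "a prospective observational study with data collection from a single center", "for a period that ranges October 2020-December 2021". The list of inclusion criteria follows directly.
- **Patient Selection** uses the same months for treatment: "Between October 2020 and December 2021, and expected number of 30 patients will be treated".
- **Hypothesis** sets the rule for each patient: "Patients will be evaluated starting from the date of inclusion as candidates for TACE treatment, and followed up for 6 months", with one qualification, "unless patients are lost to clinical follow-up or death occurs". Laboratory values "will be evaluated at the following time-points: pre-embolization, at one month, three months, and six months", and CT or MRI follows the same schedule. On the data source it says "The information will be collected through the electronic database of the patient".
- **Objectives and End-points** times objective response rate (ORR), disease control rate (DCR) and adverse events as "Assessed at 1, 3, and 6 months after first treatment". ORR and DCR are taken over all cases.

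The visible text names no data cut-off, no database closure and no separate end of follow-up. The flowchart is not shown, so nothing is inferred from it.

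**The concern.** Treatment and data collection cannot both end in December 2021 if a patient treated late in that year is to have a 6-month scan. Read on its own, the Study Proposal sentence attaches the dates to data collection. Someone who set the closing date from that sentence alone would lose the 6-month assessment of everyone treated after about June 2021.

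The ORR and DCR definitions make this look worse. With all cases in the denominator, a patient without a 6-month scan either counts as a non-responder, so that the calendar pulls the rate down, or is left out, which departs from the stated denominator. Adverse events at 6 months would also be unobserved in the later patients. Technical success and non-target embolization would not be touched, because they are assessed at or just after the procedure.

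**Working it through.** The figure of 30 is an expected count without a power or precision calculation, so there is no sample-size figure to reproduce. The check is calendar arithmetic, followed by a comparison of the two readings.

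**Inputs from the protocol.** Window October 2020 to December 2021, which is 15 calendar months (Study Proposal, Patient Selection); 30 patients (Patient Selection); assessments at m = 1, 3 and 6 months (Hypothesis, Objectives and End-points).

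**Inputs assumed.** A hard stop at the end of December 2021. Cumulative accrual (t/15)^k, with k = 0.5 (front-loaded), 1 (even) or 2 (back-loaded). Patients without a scan stay in the denominator as non-responders.

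**Reading A: December 2021 ends data collection.** The share of patients who reach month m is ((15 − m)/15)^k. This is also the highest ORR or DCR that could be reported over all 30. The number missing is 30 × (1 − share).

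| Visit | (15 − m)/15 | k = 0.5 | k = 1 | k = 2 |
|---|---|---|---|---|
| 1 month | 14/15 | 97% (1.0 missing) | 93% (2.0) | 87% (3.9) |
| 3 months | 12/15 | 89% (3.2) | 80% (6.0) | 64% (10.8) |
| 6 months | 9/15 | 77% (6.8) | 60% (12.0) | 36% (19.2) |

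Counting days instead of months changes little. With even accrual from 1, 20 or 31 October 2020 to 31 December 2021 (457, 438 or 427 days), the share treated by 30 June 2021 is 273/457 = 0.597, 254/438 = 0.580 or 243/427 = 0.569.

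If patients without a scan were left out instead, there would be no cap. Under even accrual the 6-month rate would rest on 18 patients, and its standard error would be larger by a factor of √(30/18) = 1.29.

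**Reading B: December 2021 ends treatment, and each patient is then followed for 6 months.** Collection runs to about June 2022, 15 + 6 = 21 months in all. All 30 patients can reach month 6 and the calendar loss is 0.

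The loss is also 0 under Reading A if all 30 are treated by the end of June 2021. That needs 30/9 = 3.3 patients per month instead of 30/15 = 2.0.

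**Which reading fits the text.**

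- Patient Selection ties these months to treatment in so many words. Reading B takes that literally.
- Hypothesis allows follow-up shorter than 6 months only after loss to follow-up or death. Reading A adds a third reason, the calendar, which the protocol does not provide for. Reading B adds none.
- The 6-month assessments in Hypothesis and in Objectives and End-points can be made for every patient under Reading B. Under Reading A they can be made only if accrual finishes early.
- The Study Proposal sentence is the one place where Reading A has the more literal claim. It is a general description of the study that leads into eligibility, and it says nothing about closing the database.
- The source is the electronic patient record. Nothing in the text prevents it from being read in 2022.

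**The case for a change.** The strongest case for a change is that Reading B has to be inferred. The words in Study Proposal attach the dates to data collection, no visible sentence says that collection continues afterwards, and the study period is something a protocol should state clearly. Rewording would cost two sentences and no extra patients or procedures, whereas a wrong closing date could remove 6-month efficacy and safety data for a sizeable share of a 30-patient study.

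Part of this stands. The sentence is loose, the two periods are quoted correctly, and the arithmetic under a hard stop is right. What does not stand is the step from a loose sentence to lost data. The 6-month rule is as much part of the written protocol as the period sentence, and it is the more specific of the two. That a calendar stop would be an exception the protocol does not list is evidence that none was intended. The cap also needs an accrual curve that the protocol does not give and a particular handling of missing scans, which is commonly left to the SAP.

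A related point is that Hypothesis starts evaluation at inclusion while the endpoints run from first treatment. This is no contradiction: inclusion serves for baseline, and ORR, DCR and adverse events already have their own starting point.

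**Conclusion.** No change to the plan follows. The identical dates are a slip of wording that an analyst resolves from the protocol itself: October 2020 to December 2021 is the treatment window, and each patient is then followed for 6 months, to about June 2022. On that reading the calendar removes 0 of 30 patients from the 6-month assessments, and 6-month ORR, DCR and adverse-event data are as complete as loss to follow-up and death allow.

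The 60% ceiling (36% to 77% across the assumed accrual patterns) would apply only if three conditions held together: a hard stop in December 2021, accrual spread over the full 15 months, and patients without a scan counted as non-responders. The visible text states no such stop, gives only the treatment window for accrual, and does not say how a missing scan is counted. The conclusion rests on the per-patient follow-up rule prevailing over the general period sentence; the flowchart, which is not shown, could not be consulted.

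### The lipase/amylase sentence contradicts itself on timing, and the readable protocol lists no liver test between the procedure and one month, so short-lived grade 3 rises may go uncounted

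*Protocol*

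**What the plan says.** All of the laboratory follow-up is set out in one paragraph of the Protocol's HYPOTHESIS section. A single sentence names AST, ALT, ALP, bilirubin, albumin and the blood count, adds "as well as serum lipase and amylase levels within the 1st week post-TACE to detect pancreatitis, will be evaluated at the following time-points", and gives the list as "pre-embolization, at one month, three months, and six months". Imaging hangs on the same list: "Computed tomography (CT) or Magnetic Resonance Imaging (MRI) with contrast will be performed at the same time-points as just indicated".

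The same section says "All serologic toxicities would be classified according to common terminology criteria for adverse effects", and adds that "severe hepato-toxicity (grade 3) is classified as the increase of up to 5 times the normal limit of AST, ALT, FA", or a bilirubin rise above a stated level. FA is read here as ALP. On the data source it says "The information will be collected through the electronic database of the patient (includes laboratory data").

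Under OBJECTIVES AND END-POINTS, the first safety item is "Adverse Events (AEs) and Serious Adverse Events (SAE) [Time Frame: Assessed at 1, 3, and 6 months after first treatment". PATIENT SELECTION gives the size of the study: "expected number of 30 patients will be treated".

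**The concern.** There are two linked problems. First, the sentence places lipase and amylase in the first week and then ties them to a list with no first-week entry. Whoever collects the data has no clear instruction for the sample meant to detect pancreatitis, which is a named safety event.

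Second, the first-week phrase attaches only to those two enzymes. The liver tests that define grade 3 hepatotoxicity have no listed draw until one month, and the adverse-event time frame starts no earlier. A rise that appears and settles within that month would not be seen at any listed draw. It would be counted only in patients who happened to have an earlier result on record. Missed events can only lower the count, in a study with safety in its title and a rationale built on sparing non-target tissue while allowing maximum doxorubicin doses.

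**Working it through.** The protocol gives no figure to reproduce here. The check is a comparison of time-points, followed by simple counts.

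**Inputs.**
- Laboratory list (HYPOTHESIS): before the procedure, then 1, 3 and 6 months.
- Lipase/amylase window (HYPOTHESIS): first week.
- Tests used for grade 3 (HYPOTHESIS): AST, ALT, FA (read as ALP) and bilirubin.
- Adverse-event assessments (OBJECTIVES AND END-POINTS, Safety): 1, 3 and 6 months after first treatment.
- Patients (PATIENT SELECTION): 30 expected.

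**Step 1: lipase and amylase.** Listed points = 4, of which 3 follow the procedure. Listed points in the first week = 0. The window and the list cannot both apply to these two tests. Taken literally, the early sample has no slot. Taken sensibly, it has a window but no stated day.

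**Step 2: liver tests.** The first-week phrase does not cover them under either reading. Listed liver-test draws after the procedure and before one month = 0. The earliest listed adverse-event assessment is also at one month, so it adds no earlier point.

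**Step 3: size.** An under-count would need three quantities: how often grade 3 rises occur, how many resolve before one month, and how many patients have an early result on record. The protocol gives none of them, so no under-count is computed. The only scale available is 1/30 = 3.3 percentage points off the reported rate for each patient whose event is missed. That is true of any event in 30 patients and is not an estimate of this problem.

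**Step 4: cost of adding the four liver tests to a first-week sample.**
- One sample per patient: 4 × 30 = 120 assays.
- If every patient also had one sampled retreatment: 4 × 60 = 240 assays. The number of retreatments is an assumption, because the protocol gives none.

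**The case against.** The best reply is that the lipase/amylase clash is drafting. A first-week test cannot be done at one, three or six months, so only one sensible reading is left. That stands: this part is a wording repair. A reader might infer that no early pancreatic sample is planned, but the text does not support that, since it names both the window and its purpose.

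The second reply is that the flowchart is not visible and may show an early visit. That also stands, and it makes the liver-test gap a finding about the readable text only.

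Third, the instruction to classify toxicities covers all serologic ones, and data come from the electronic record, so earlier values may be captured and graded. This stands in part. The text neither requires early liver tests nor says whether unscheduled values count, so detection could depend on who happened to be tested. The later reference to routine clinical practice, under DEB-TACE PROCEDURES, concerns the embolization and not laboratory follow-up.

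Fourth, the stakes are modest. The safety endpoints do not name a hepatotoxicity rate and no test depends on one; it enters through the grading rule. This is correct and limits the weight of the point.

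Finally, the ambiguous multiple-of-normal threshold is a separate matter of definition. Agreed: it lends no support to the timing argument and is dealt with on its own below.

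**Conclusion.** The concern holds in a limited form. The sentence on lipase and amylase is internally inconsistent and must be reconciled. In the readable text, AST, ALT, ALP and bilirubin have no listed draw between the procedure and one month, although grade 3 hepatotoxicity is graded on them. Any error from this gap runs one way, towards too low a count, by an amount the document does not allow to be computed.

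A reader might go further and infer that hepatotoxicity will be under-reported. The document does not support that: it gives no time course for such rises, does not show the flowchart, and allows earlier values to come from the record. If early liver tests are uniform at this centre and are counted, only the wording needs repair. The change is still worth making because it is cheap and the gap works in one direction.

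Separately, the grade 3 rule on enzyme multiples can be read as a ceiling or as a minimum. The two readings grade different patients, and that ambiguity could move the count either way.

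**What to change.** Unless the flowchart already schedules early liver tests:

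- List the first-week lipase/amylase sample as its own time-point, record the sampling day, and run AST, ALT, ALP and bilirubin on that same sample.
- Word the change so that CT/MRI stays at the existing four time-points, because imaging is defined by reference to the laboratory list.
- Grade hepatotoxicity on the worst post-baseline value, including earlier values in the electronic record. Report beside it the rate at the listed draws alone and the number of patients with any liver test before one month.
- State whether the first-week sample is repeated after a retreatment.

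As a separate correction, reconcile the multiple-of-normal wording with the toxicity scale it refers to, so that it is clear which values count as grade 3.

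The cost is a wording change and about 120 assays for 30 patients, or 240 under the retreatment assumption above. If no first-week sample was in fact intended, it also means one extra blood draw per procedure. The reported toxicity rate may rise. Worst-value grading gives patients with more recorded results more chances to count, which is why the listed-draw rate belongs beside it. A single first-week sample may still miss very short rises.

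### The grade 3 hepatotoxicity rule takes no account of the pre-embolization value: its bilirubin limit equals the entry ceiling, and its enzyme limit has no matching entry ceiling.

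*Protocol*

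**What the plan says.** The inclusion criteria (Protocol, STUDY PROPOSAL) require "Bilirubin less than 3 gr/dl". They list no limit for AST, ALT or ALP. The contraindications include "Advanced liver disease", without a numeric definition.

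The toxicity paragraph (Protocol, HYPOTHESIS) states that "All serologic toxicities would be classified according to common terminology criteria for adverse effects"; no version is given. It then fixes the severe category itself: "severe hepato-toxicity (grade 3) is classified as the increase of up to 5 times the normal limit of AST, ALT, FA", or an "increase of bilirubin level to over 3 g/dl". Neither limit refers to the patient's pre-embolization value.

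The same paragraph does plan to look at "Changes in the serum levels of aspartate aminotransferase (AST), alanine aminotransferase (ALT), Alkaline phosphatase (ALP), bilirubin, albumin" and other laboratory values, and these "will be evaluated at the following time-points: pre-embolization, at one month, three months, and six months". The baseline is therefore collected and changes are examined, but the grade 3 rule uses neither.

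**The concern.** A severity grade in a study of a liver-directed treatment should separate what the treatment did from what the patient brought to it. The protocol's BACKGROUND says that "Liver cirrhosis is the main risk factor for developing HCC", so abnormal values before embolization are foreseeable. The study is a single-centre observational series and describes no control group, so background liver disease cannot be subtracted by comparison.

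If the severe limit begins where eligibility ends, the severe rate depends partly on how many patients enter close to the limit. A small movement in one patient is labelled severe and a much larger one in another is not. For the enzymes, two readers could score the same patient differently, because the text does not say how to treat a value that was already above the limit.

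**Working it through.** The plan gives no expected hepatotoxicity rate, so there is no figure to reproduce. The check sets the entry and grade 3 limits side by side.

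**Inputs from the protocol.** Bilirubin at entry below 3 (STUDY PROPOSAL). Grade 3 above 3 (HYPOTHESIS). Follow-up values at 1, 3 and 6 months (HYPOTHESIS). Expected patients: 30 (PATIENT SELECTION). The bilirubin unit is printed as gr/dl at entry and g/dl in the toxicity rule. The arithmetic below assumes that one unit is meant in both places; which one does not matter to it.

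**Step 1: rise needed to reach the limit.** Rise = 3/baseline − 1.
- From 2.9: 3/2.9 − 1 = 3.4%
- From 2.5: 3/2.5 − 1 = 20%
- From 2.0: 3/2.0 − 1 = 50%
- From 1.5: 3/1.5 − 1 = 100%
- From 1.0: 3/1.0 − 1 = 200%

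A move from 2.9 to 3.1 (0.2/2.9 = 6.9%) is grade 3. A move from 1.0 to 2.9 (1.9/1.0 = 190%) is not.

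**Step 2: crossings with no treatment effect (illustration).** Suppose a patient's bilirubin varies lognormally around a stable level L with within-patient coefficient of variation CV. For one visit, P = 1 − Φ(ln(3/L)/s), with s = √ln(1 + CV²). Over three visits, taken as independent, the chance of at least one value above 3 is 1 − (1 − P)³. CVs of 10%, 20% and 30%, the lognormal form and independence are assumptions; none is in the protocol.

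Example: L = 2.5, CV = 20%. s = √ln(1.04) = 0.198; ln(3/2.5) = 0.182; P = 1 − Φ(0.92) = 0.179; 1 − 0.821³ = 0.446.

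| Stable level | One visit, CV 10/20/30% | Any of three, CV 10/20/30% |
|---|---|---|
| 1.0 | about 0% in all | about 0% in all |
| 1.5 | 0 / 0 / 1% | 0 / 0.1 / 2.7% |
| 2.0 | 0 / 2 / 8% | 0 / 6 / 23% |
| 2.5 | 3 / 18 / 27% | 10 / 45 / 61% |
| 2.8 | 24 / 36 / 41% | 57 / 74 / 79% |

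If values at successive visits are positively correlated, the chance over three visits lies between the two columns. The effect is negligible for patients who enter near 1 and large only close to the ceiling.

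**Step 3: weight of one case.** 1/30 = 3.3% (exact 95% confidence interval 0.1% to 17.2%); 2/30 = 6.7%; 3/30 = 10%.

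**Step 4: enzymes.** Read the limit as more than 5 times the normal limit, and take a patient with a value of 6 times before embolization and at all three visits. If the rule is read as a level, the patient is grade 3 at each visit. If it is read strictly as an increase, the patient never is. The entry criteria do not exclude such a patient by number, and the text does not choose between the readings.

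**Step 5: the enzyme wording.** Taken literally, the phrase in "severe hepato-toxicity (grade 3) is classified as the increase of up to 5 times the normal limit of AST, ALT, FA" sets an upper bound: a value of 2 times the normal limit would qualify and one of 8 times would not. A severity limit needs a lower bound. FA is taken here to mean the ALP of the laboratory list, which is also an assumption.

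**The case against.** The strongest reply is that the rule already demands something new. Entry is below 3 and grade 3 requires an increase to above 3, so a reader who infers that an unchanged baseline bilirubin is recorded as severe toxicity goes too far: at the qualifying value nobody can be grade 3. This stands. What remains for bilirubin is that the required rise can be trivial.

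A reader might also infer that the plan ignores the baseline altogether, or that raised enzymes will be scored as toxicity at every visit. The documents support neither. Values are taken before embolization, changes are evaluated, both limits are worded as an increase, and the safety section speaks of emerging events. That cover is partial, because the grade 3 sentence uses none of it and the safety bullet applies a different (JVIR) classification. For enzymes the right word is 'could'.

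Nor is a rise from 1.0 to 2.9 lost: all serologic toxicities are graded and changes are examined. It is only kept out of the severe category.

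Hepatotoxicity is not named among the safety items in OBJECTIVES AND END-POINTS, so it should not be called a main safety result.

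Finally, shift tables are commonly left to a statistical analysis plan, which is not shown, and their absence from the protocol is no fault. The point rests on the rule that the protocol itself fixes.

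**Conclusion.** The point holds in limited form. The grade 3 bilirubin limit and the entry ceiling are the same number, so the rise that earns a severe grade ranges from about 3% (entry at 2.9) to 200% (entry at 1.0). The enzyme limit is tied to the normal limit with no entry ceiling listed, so a value already high before embolization could be counted, depending on how 'increase' is read. With 30 patients and no control group described, this can mix background liver disease into the severe rate.

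The overall size cannot be given. Each affected patient is 3.3 percentage points, but how many will enter near 3 is unknown, and the exclusion of advanced liver disease may keep that number small. The crossing probabilities rest on assumed variation and only illustrate where the problem lies. The protocol should be corrected, but the laboratory data to be collected remain usable.

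**What to change.** Keep the absolute-limit rate and add the following to the toxicity paragraph or the analysis plan:

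1. Severe hepatotoxicity is attributed to treatment only when the grade is worse than the patient's own pre-embolization grade. This settles the enzyme ambiguity.
2. For each analyte, a shift table from pre-embolization grade to worst post-treatment grade.
3. For every grade 3 case, the baseline value with the absolute and percentage change; for all patients, a summary of change from baseline. This part is needed because item 1 alone still counts a move from 2.9 to 3.1 and still leaves 1.0 to 2.9 outside the severe category. With it, both are visible.
4. In the same sentence, word the enzyme limit as a lower bound, use one abbreviation for alkaline phosphatase, and reconcile the bilirubin unit here and in the inclusion criteria with the unit the laboratory reports.

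No visit, sample or treatment changes, since all the values are already scheduled. The cost is a few sentences, one extra table and a second rate that is less directly comparable with series using absolute limits, which is why the absolute-limit rate stays beside it.
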